## Proportion of subjects remain in an outpatient setting and maintain SpO2 >94%

Subjects remain in an outpatient setting is defined as no hospitalization or ICU admission through Day 3, Day 7, and Day 14.

In the case when multiple  $SpO_2$  values are recorded on the same day, e.g.  $SpO_2$  values from subject self-reported at home and from healthcare provider visit on the same day, the lower value will be used for the analysis.

The proportion of subjects who remain in an outpatient setting and maintain  $\text{SpO}_2 \ge 94\%$  on room air at each timepoint within each treatment group will be presented along with a two-sided exact (Clopper-Pearson) 95% CI.

The observed difference in the proportion of subjects who remain in an outpatient setting and maintain  $\text{SpO}_2 \ge 94\%$  on room air at any timepoint between each C19-IG 20% dose group and placebo along with the exact unconditional 95% CI for risk difference will be calculated. The null hypothesis will be tested using Chi-square statistic and the p-value will be reported.

### Proportion of subjects negative for SARS-CoV-2 by PCR through Day 14 and Day 29

The proportion of subjects with negative SARS-CoV-2 by PCR through Day 14 and Day 29 within each treatment group will be presented along with a two-sided exact (Clopper-Pearson) 95% CI.

At each time point, the observed difference in the proportion of subjects with negative PCR test results between each C19-IG 20% dose group and placebo along with the exact unconditional 95% CI for risk difference will be calculated. The null hypothesis will be tested using Chi-square statistic and the p-value will be reported.

### Time to negative SARS-CoV-2 PCR from Baseline through Day 29

The time from baseline to the first occurrence of negative SARS-CoV-2 by PCR through Day 29 will be estimated using the Kaplan-Meier (KM) method. The KM estimates along with 95% CI, and survival curves will be provided. Based on the KM estimates, the probabilities of achieving negative SARS-CoV-2 by PCR and associated 95% CIs on Days 14 and 29 will be reported; in addition, the 25th, 50th (median), and 75th percentiles of the time to negative SARS-CoV-2 by PCR with associated 95% CIs will be provided, as data permit. The survival rates between each C19-IG 20% dose group and placebo will be compared using Log-rank test. The p-value from Log-rank test will be presented.

### Proportion of subjects requiring O2 supplementation on or before Day 29

The proportion of subjects requiring oxygen supplementation through Day 29 within each treatment group will be presented along with a two-sided exact (Clopper-Pearson) 95% CI.

The observed difference in the proportion of subjects requiring oxygen supplementation between each C19-IG 20% dose group and placebo along with the exact unconditional 95% CI for risk difference will be calculated. The null hypothesis will be tested using Chi-square statistic and the p-value will be reported.

### Duration of any oxygen use through Day 29

The duration (number of Days) of any oxygen use from Day 1 through Day 29 will be calculated based on the start/stop date of using oxygen supplementation recorded on the eCRF All Visits page "General Duration of Hospitalization, & Overall Requirement for Mechanical Ventilation, ICU Admission and/or Oxygen Supplementation". Number of days on oxygen will be compared between each C19-IG 20% dose group and placebo using an ANCOVA model, including number of days on oxygen as a dependent variable, treatment group as a fixed effect, and baseline characteristics such as age and gender as covariates. From this model, the LS means and 95% CIs for each treatment group, the treatment difference in the LS means, the 95% CI for the difference, and the associated p-value will be presented.

In the event the data is highly skewed, e.g. very few subjects received supplemental oxygen, a sensitivity analysis using a non-parametric Wilcoxon Rank Sum test will be performed. The p-value from Wilcoxon Rank Sum test, as wells as the Hodges-Lehmann estimate of the treatment difference and the corresponding 95% CI will be provided.

Subjects who died during the hospitalization without a stop date of using oxygen supplementation recorded on the eCRF will be assigned as being on oxygen for the number of days remaining to Day 29 for the analysis. Subjects who had oxygen use ongoing at study completion will be assigned an oxygen use end date equals to the date of completion for the purpose of deriving duration of oxygen use. Subjects who never received supplemental oxygen through Day 29 will be included in the analysis with a value of zero days of oxygen use.

A listing of all supplemental oxygen and saturation (SpO2 and SaO2) data collected from both subject self-monitoring at home and health provider visits will be provided.

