	Number	BIG-CL-PRT-000028	Version	5.0	Status	Effective	Effective Date	13-Oct-2021
	GC2010 - A Multi	Multicenter, Randomized, Double-blind,	, Parallel Gro	up Study to I	evaluate the Sa	fety and Efficacy of		0073
Anti-COVID-19 Immune	Anti-COVID.	-19 Immune Globulin (Human) 20% (C19	9-IG 20%) ve	rsus Placebo	in Asymptoma	tic Ambulatory	Page	68 of 106

- artery disease, or cardiomyopathies; Immunocompromised state from solid organ transplant; Obesity (body mass index [BMI] of 30 kg/m2) or higher; Diabetes mellitus
- Respiratory sample for quantitative measurement of SARS-CoV-2 viral load by NAT or PCR (real-time RT-PCR) (obtained via nasopharyngeal swab)
- Sample for quantitative measurement of IgM and IgG antibodies to SARS-CoV-2 by
  enzyme linked immunosorbent assay (ELISA), indirect fluorescent antibody (IFA), or
  another assay methodology (store *serum* samples frozen at -70°C for later analysis at an
  external lab)
- Serum Chemistry (creatinine, albumin, ALT, total bilirubin, LDH)
- Hematology: absolute neutrophil & lymphocyte count and standard hematology (hemoglobin, hematocrit, platelet count, leukocyte count with differential)
- Ferritin (serum), D-dimer (plasma, sodium citrate tube), CRP (serum)
- Sample for IL-6, interferon γ, and possibly autoantibodies against type 1 interferons.
   Note: serum samples must be stored at -70°C for later analysis at a reference laboratory.
- Sample for possible additional quantitative neutralizing antibody versus SARS-CoV-2 (serum sample reserved for neutralizing antibody testing if such testing becomes feasible stored frozen at -70°C for later analysis at an external lab).
- Pregnancy test for females of child-bearing potential (human chorionic gonadotropin [hCG] based assay [urine matrix also valid])
- Record SAEs and TEAEs
- Record concomitant medications
- Provide subjects with pulse oximeter for home use and SpO2 monitoring on room air (train subjects in use of pulse oximeter).
  - O Please note: Whilst at home, subjects are to record SpO2 using a pulse oximeter (self-monitoring at home daily) from Day 1 when they receive their pulse oximeter through the Healthcare Provider Visit on Day 14. Likewise, subjects are to measure and record body temperature (non-axillary) and whether any antipyretic was taken on each day (ie, self-monitoring at home daily) throughout this same period.

After all Screen/Baseline assessments are complete subjects may be randomized.

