### 6.2 Secondary Efficacy Endpoints and Analyses

### Change in SARS-CoV-2 viral load

Change in SARS-CoV-2 viral load (log10 copies/mL) from Baseline to Day 7 and to Day 14 will be compared between each C19-IG 20% dose group and placebo using the analysis of covariance (ANCOVA) model, including the change from baseline value as a dependent variable; treatment group as a fixed effect; and baseline SARS-CoV-2 viral load value, age and gender as covariates. From this model, the LS means and 95% CIs for each treatment group, the treatment difference in the LS means, the 95% CI for the difference, and the associated p-value will be presented at Day 7 and Day 14.

Subgroup analyses based on the presence of comorbidities associated with increased risk of serious

COVID-19 will be performed on change in SARS-CoV-2 viral load using the method described above with ANCOVA model at Day 7 and Day 14. If data permit, a subgroup analysis based on the number of comorbidities (<2 comorbidities vs. >=2 comorbidities) will also be performed.

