#### **Table 2 Sample Size Estimation**

[Sample sizes in table were calculated using https://www.sealedenvelope.com/power/binary-superiority/]

Based on the above extrapolation/estimate, and allowing for a total of 3 arms, randomized 1:1:1 to Placebo and 2 dose levels of C19-IG 20% approximately 801 subjects are allowed to be randomized as part of a humanitarian effort against COVID-19. N=267 subjects per group should allow differentiation in disease evolution for patients randomized to C19-IG 20% versus the control Placebo arm.

Sample size estimation was also calculated with regard to consideration of the viral load first secondary endpoint. A sample size of ~172 patients/arm would theoretically provide the trial with 80% power to detect a difference of 0.5 log10 in the mean reduction of SARS-CoV-2 viral load at a two-sided significance level of  $\alpha = 0.025$ , assuming an expected standard deviation of 1.5 . A 0.5 log10 copies/mL difference in reduction was chosen to represent the minimal threshold for a

biologically relevant change for analyses based on analogy with other viruses. However, it is unknown whether this degree of viral load reduction will be realized as a result of the planned dosages of C19-IG 20% within this clinical setting. The larger sample size per arm provides a greater level of assurance in this regard.

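### Time to negative PCR and proportion PCR-negative are tested without the Day 1 viral load; stratifying on it is free and may recover some power (about 0 to 11 points, by assumption)

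*SAP*

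**What the plan says.** SAP 6.2 has three analyses built on the nasopharyngeal swab series.

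- Change in viral load to Day 7 and Day 14: ANCOVA with "baseline SARS-CoV-2 viral load value, age and gender as covariates".
- Proportion PCR-negative: "At each time point, the observed difference in the proportion of subjects with negative PCR test results between each C19-IG 20% dose group and placebo" is reported with an exact interval and tested by chi-square, with no covariate or stratum.
- Time to negative PCR through Day 29: Kaplan-Meier estimates, then "The survival rates between each C19-IG 20% dose group and placebo will be compared using Log-rank test". Under SAP 4.6 the event is the first negative result.

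Protocol 7.2.2 lists this among the assessments before dosing: "Respiratory sample for quantitative measurement of SARS-CoV-2 viral load by NAT or PCR (real-time RT-PCR) (obtained via nasopharyngeal swab". Footnote f of the schedule requires the Day 1 samples from all patients before the infusion. Randomization is stratified by age group only (SAP 3.2.1). Protocol 9.1 names the log-rank test for time-to-event variables and allows Fisher, chi-square or CMH for proportions.

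**The concern.** A subject turns PCR-negative when the load falls below the assay limit, so the starting load is a natural predictor of when that happens. Entry accepts a positive PCR or antigen test on a specimen up to 5 days old (Protocol 5.1), and no criterion sets a minimum Day 1 load. Subjects may therefore enter at quite different points of viral decline. If so, the spread in starting load is noise in an unadjusted comparison of clearance, and a chance imbalance in Day 1 load is left in it. The clearance results could then differ from the adjusted viral-load result obtained from the same swabs. At stake is power on two secondary endpoints, not their validity.

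**Working it through.** **1. The plan's own figure.** SAP 10 states: "A sample size of ~172 patients/arm would theoretically provide the trial with" 80% power for a 0.5 log10 difference, "assuming an expected standard deviation of 1.5", at two-sided 0.025. The formula is n = 2 × (SD/difference)² × (z(1−α/2) + z(power))². With the numbers, 2 × (1.5/0.5)² × (2.241 + 0.842)² = 18 × 9.505 = 171.1, so 172 per arm. This reproduces exactly. It is a calculation for mean reduction in load, the endpoint that ANCOVA already adjusts. No power, effect size or event rate is given for either clearance endpoint.

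**2. Why the SD and the effect do not settle the gain.** For a continuous outcome, adjustment for a covariate with correlation ρ shrinks the SD by √(1−ρ²). As an analogue:

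- n = 172, two-sided 0.025: 80.2% unadjusted; gain 1.7 points at ρ = 0.2, 6.9 at 0.4, 10.6 at 0.5.
- n = 240 (267 less 10% withdrawal), two-sided 0.05, the level SAP 4 uses for testing: 95.5% unadjusted; gain 0.7, 2.4 and 3.3 points at the same ρ.

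The answer moves with ρ, n and alpha, and ρ is not in the documents.

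**3. Simulation of the clearance endpoints.** From the documents: 240 per arm, two-sided 0.05, swabs on Days 3, 7, 14 and 29, a 0.5 log10 shift, SD of change 1.5. Assumed: mean baseline load 6 or 7 log10, baseline SD as shown, mean daily decline 0.35 or 0.40 with SD 0.19, assay SD 0.7, detection limit 2 log10, full shift from Day 7 and one third of it at Day 3. Over the six days from Day 1 to Day 7 the SD of change is √((0.19 × 6)² + 2 × 0.7²) = √(1.30 + 0.98) = 1.51, which matches the plan.

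Gain in power, in percentage points, for the log-rank test stratified by baseline-load quartile over the plain log-rank test. Ranges cover repeated runs with slightly different settings; Monte Carlo error is about 1 to 2 points.

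| Correlation of baseline load with rate of decline (assumed) | Baseline SD 1.0 | SD 1.5 | SD 2.0 |
|---|---|---|---|
| 0 | 1 to 3 | 5 to 9 | 8 to 11 |
| 0.3 | 1 | 4 | 8 |
| 0.5 | 0 to 1 | 1 to 2 | 4 to 6 |

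With decline independent of baseline, plain log-rank power was about 28% to 42% across these SDs. For the Day 14 proportion, CMH by quartile gained about 3 to 7 points over chi-square at SD 1.5 to 2.0 under independence. A further run that also covered correlation 0.5 gave 0 to 5. Null rejection for all four tests lay between 4.7% and 5.7%.

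**4. A different model.** Here placebo negativity was set at 10%, 25%, 50% and 85% on the four swab days.

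- If 1.5 is the SD of the follow-up load, plain log-rank power is about 91% and chi-square about 82%. For ρ from 0 to 0.7, adjustment gains about 0 to 8 and 0 to 12 points.
- If 1.5 is the SD of change at every visit and change is independent of baseline, the stratified log-rank test gains about 10, 22 and 34 points at baseline SD 1.0, 1.5 and 2.0, and a model with continuous adjustment up to 43. This reading ties baseline to every later load, Day 29 included, with correlation SD/√(SD² + 1.5²) = 0.55, 0.71 and 0.80.

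In step 3 the link weakens over time because decline rates differ. At Day 14 with baseline SD 1.5 it is 1.5² / (√(1.5² + 0.7²) × √(1.5² + (0.19 × 13)² + 0.7²)) = 2.25/(1.66 × 2.97) = 0.46.

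**The case against.** The strongest reply is that nothing is wrong. Under randomization the plain log-rank and chi-square tests are valid, and the simulated type I error agrees. Both endpoints sit outside the multiplicity hierarchy (SAP 4.5), and neither is on the futility list (SAP 9). A baseline-adjusted analysis of the same swabs is already the first secondary endpoint. SAP 6.2 also follows a recognizable pattern in line with Protocol 9.1: models with the baseline value for continuous change, chi-square for proportions, log-rank for times. All of this stands, and it limits the point to efficiency.

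The gain may also be negligible. If subjects with higher loads clear virus faster, baseline load predicts time to negativity poorly, as the last row of the table shows. The documents do not exclude that.

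A reader might infer that the clearance endpoints are singled out as the only ones analysed without their own baseline. They are not. The proportional-odds model for the ordinal scale names only optional age and gender, and the SpO2 proportion is tested by plain chi-square although saturation is recorded at screening.

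What the reply does not meet is that the covariate is already collected and already used in the same section, and that stratifying on it leaves type I error unchanged.

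**Conclusion.** The point holds as an efficiency gain. Both PCR-clearance tests leave out a pre-dose covariate planned in every subject, and they lose power to the extent that it predicts clearance. At 240 per arm and two-sided 0.05, with an assumed baseline SD of 1.0 to 2.0 log10, the decline-rate simulations give about 0 to 11 points for time to negative PCR and about 0 to 7 for the Day 14 proportion. The gain is near zero at a baseline SD of about 1.0 or if higher loads decline faster.

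A reader might infer that the plan's SD of 1.5 and its 0.5 log10 difference fix a definite loss, for example 6 to 11 points. They do not: both belong to the endpoint that is already adjusted, and the result needs a baseline SD, a clearance rate or detection limit, and a correlation, none of which the documents give. The 0 to 11 range is therefore not a bound. The last model in the check gives more, on an assumption that the documents neither state nor exclude. This is a free improvement to consider; the planned tests are not in error.

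**What to change.** Amend SAP 6.2 before unblinding:

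- Test time to negative PCR with a log-rank test stratified by quartile of Day 1 viral load, with cut points taken from all arms pooled.
- Test the proportion PCR-negative by CMH on the same strata and report the common risk difference, as SAP 6.1 already does for the primary sensitivity analysis.
- Put undetectable Day 1 loads in the lowest stratum. They are possible, since the qualifying test may be up to 5 days old.
- Put missing Day 1 loads in a separate stratum.
- Keep the unadjusted Kaplan-Meier curves and raw proportions as description.

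The cost is SAP wording and programming, with no new data, visits or patients. Protocol 9.1 already allows CMH for proportions, and a stratified log-rank test stays within the method it names for times to event. The change should be entered in the SAP revision table.

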### 2.2.2 Secondary Efficacy Endpoints

The secondary efficacy endpoints include the following:

- Change in SARS-CoV-2 viral load (log10 copies/mL) from Baseline (Day 1) to Day 7 and to Day 14.
- Proportion of subjects who remain in an outpatient setting and maintain SpO2 ≥94% on room air on Day 3, Day 7, and Day 14.
- Proportion of subjects negative for SARS-CoV-2 by PCR at multiple time points through Day 14 and through Day 29.
- Time to negative SARS-CoV-2 PCR from Baseline through Day 29.
- Proportion of subjects who require O2 supplementation on or before Day 29.
- If requiring supplemental oxygen post randomization: Duration of any oxygen through Day 29.
- Absolute value and mean change from baseline in the 7-point Ordinal scale Day 1, Day 7, Day 14, and Day 29:

The 7-point Ordinal scale is as follows:

1) Death;

- 2) Hospitalized, on invasive mechanical ventilation or extracorporeal membrane oxygenation (ECMO);
- 3) Hospitalized, on non-invasive ventilation or high flow oxygen devices;
- 4) Hospitalized, requiring supplemental oxygen;
- 5) Hospitalized, not requiring supplemental oxygen;
- 6) Not hospitalized, limitation on activities;
- 7) Not hospitalized, no limitations on activities.
- Proportion (percentage) of subjects in each severity category of the 7-point Ordinal scale at Day 1, Day 7, Day 14, and Day 29.
- Assessment of Clinical Severity: Change in NEWS from baseline (at Day 7, Day 14, and Day 29).

The NEWS has demonstrated an ability to discriminate patients at risk of poor outcomes. This score is based on 7 clinical parameters (respiration rate, oxygen saturation, any supplemental oxygen, temperature, systolic blood pressure, heart rate, level of consciousness [Alert, Voice, Pain, Unresponsive]).

- Proportion of subjects who require at least one COVID-19 related medically attended visit for management/treatment of COVID-19 (apart from routinely scheduled study-directed visits) which may occur in any setting through Day 29 (e.g., Emergency department, urgent care, outpatient clinic or professional setting wherein direct in-person/telemedicine medical assessment and escalation of care for COVID-19 is provided by licensed healthcare personnel).
- Proportion of subjects who require hospital admission for medical care (non-quarantine purpose) through Day 29.

- If admitted to hospital post randomization: Duration of hospital stay through Day 29.

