### **Duration of Hospitalization through Day 29**

The duration (number of days) of hospitalization from post-randomization through Day 29 will be calculated based on hospital admission and discharge dates recorded on the eCRF. Number of days in the hospital will be compared between each C19-IG 20% dose group and placebo using an ANCOVA model, including number of days in the hospital as a dependent variable, treatment group as a fixed effect, and baseline characteristics such as age and gender as covariates. From this model, the LS means and 95% CIs for each treatment group, the treatment difference in the LS means, the 95% CI for the difference, and the associated p-value will be presented.

In the event the data is highly skewed, e.g. very few subjects hospitalized, a sensitivity analysis using a non-parametric Wilcoxon Rank Sum test will be performed. The p-value from Wilcoxon Rank Sum test, as wells as the Hodges-Lehmann estimate of the treatment difference and the corresponding 95% CI will be provided.

Subjects who died while in the hospital will be assigned as in the hospital for the number of days remaining from the day of death to Day 29 for the analysis. Subjects who were in the hospital at study completion will be assigned a hospitalization end date equals to the date of completion for the purpose of deriving the duration of hospitalization. Subjects who never been hospitalized through Day 29 will be included in the analysis with a value of zero days in the hospital.

#### Proportion of subjects requiring ICU admission through Day 29

The proportion of subjects requiring ICU admission through Day 29 within each treatment group will be presented along with a two-sided exact (Clopper-Pearson) 95% CI.

The observed difference in the proportion of subjects requiring ICU admission between each C19-IG 20% dose group and placebo along with the exact unconditional 95% CI for risk difference will be calculated. The null hypothesis will be tested using Chi-square statistic and the p-value will be reported.

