#### **Duration of ICU stay through Day 29**

The duration (number of days) of ICU stay from post-randomization through Day 29 will be calculated based on ICU admission and discharge dates recorded on the eCRF. Number of days in the ICU will be compared between each C19-IG 20% dose group and placebo using an ANCOVA model, including number of days in the ICU as a dependent variable, treatment group as a fixed effect, and baseline characteristics such as age and gender as covariates. From this model, the LS means and 95% CIs for each treatment group, the treatment difference in the LS

means, the 95% CI for the difference, and the associated p-value will be presented.

In the event the data is highly skewed, e.g. very few subjects admitted to ICU, a sensitivity analysis using a non-parametric Wilcoxon Rank Sum test will be performed. The p-value from Wilcoxon Rank Sum test, as wells as the Hodges-Lehmann estimate of the treatment difference and the corresponding 95% CI will be provided.

Subjects who died while in the ICU will be assigned as in the ICU for the number of days remaining from the day of death to Day 29 for the analysis. Subjects who were at ICU at study completion will be assigned an ICU end date equals to the date of completion for the purpose of deriving the number of ICU days. Subjects who never been in the ICU through Day 29 will be included in the analysis with a value of zero days in the ICU.

#### Proportion of subjects requiring invasive mechanical ventilation through Day 29

The proportion of subjects requiring invasive mechanical ventilation through Day 29 within each treatment group will be presented along with a two-sided exact (Clopper-Pearson) 95% CI.

The observed difference in the proportion of subjects requiring invasive mechanical ventilation between each C19-IG 20% dose group and placebo along with the exact unconditional 95% CI for risk difference will be calculated. The null hypothesis will be tested using Chi-square statistic and the p-value will be reported.

#### Duration of invasive mechanical ventilation through Day 29

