The duration (number of days) on invasive mechanical ventilation from post randomization through Day 29 will be calculated based on the start/stop dates of invasive mechanical ventilation recorded on the eCRF All Visits page "General Duration of Hospitalization, & Overall Requirement for Mechanical Ventilation, ICU Admission and/or Oxygen Supplementation". Number of days on invasive mechanical ventilation will be compared between each C19-IG 20% dose group and placebo using an ANCOVA model, including number of days in on invasive mechanical ventilation, treatment group as a fixed effect, and baseline characteristics such as age and gender as covariates. From this model, the LS means and 95% CIs for each treatment group, the treatment difference in the LS means, the 95% CI for the difference, and the associated p-value will be presented.

In the event the data is highly skewed, e.g. very few subjects on invasive mechanical ventilation, a sensitivity analysis using a non-parametric Wilcoxon Rank Sum test will be performed. The p-value from Wilcoxon Rank Sum test, as wells as the Hodges-Lehmann estimate of the treatment difference and the corresponding 95% CI will be provided.

Subjects who died during the hospitalization without a stop date of invasive mechanical ventilation recorded on the eCRF will be assigned as being on mechanical ventilation for the number of days remaining to Day 29 for the analysis. Subjects who had invasive mechanical ventilation ongoing at study completion will be assigned a mechanical ventilation end date equals to the date of completion for the purpose of deriving duration of mechanical ventilation. Subjects who are never placed on invasive mechanical ventilation through Day 29 will be included in the analysis with a value of zero days on mechanical ventilation.

Data collected on "Respiratory Support" eCRF through Day 60/Final Phone Check visit will be presented in a listing.

#### Mortality rate through Day 29

Subject status (Alive/Death) will be recorded in the database. If the vital status of the subject is missing, then the subject will be treated as death for the analysis.

The proportion of subjects who die through Day 29 within each treatment group will be presented along with a two-sided exact (Clopper-Pearson) 95% CI.

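### The four duration endpoints are defined for subjects who need the care but analysed as days per mITT subject with zeros, so a significant result would not show a shorter course in those requiring care

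*SAP*

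**What the plan says.** SAP 2.2.2 and Protocol 4.1.2 and 7.1.2 make the endpoint conditional on need: "If requiring supplemental oxygen post randomization: Duration of any oxygen through Day 29". Hospital stay, ICU stay and invasive ventilation are worded in the same way. All four appear again under that wording in the interim futility lists (Protocol 9.3, SAP 9).

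SAP 6.2 then keeps everyone in the analysis:

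- Oxygen: "Subjects who never received supplemental oxygen through Day 29 will be included in the analysis with a value of zero days of oxygen use".
- Hospital: "Subjects who never been hospitalized through Day 29 will be included in the analysis with a value of zero days in the hospital".
- ICU: "Subjects who never been in the ICU through Day 29 will be included in the analysis with a value of zero days".
- Ventilation: "Subjects who are never placed on invasive mechanical ventilation through Day 29 will be included in the analysis with a value of zero days".

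The comparison is an ANCOVA on number of days, with covariates such as age and gender. If the data are highly skewed, a Wilcoxon rank sum test with a Hodges-Lehmann estimate is added as a sensitivity analysis. Subjects who die in hospital or in the ICU are given the remaining days to Day 29. For oxygen and ventilation this applies when the subject dies in hospital with no stop date recorded. The proportion needing each type of care has its own chi-square test in the same section. No summary of duration restricted to users is specified.

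**The concern.** The endpoint's name promises the length of care among those who need it. The planned result is days of care per mITT subject. The two can move separately: a product may prevent admissions without shortening them, or shorten them without preventing any.

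A significant result would be filed under a name it does not support, and the quantity actually named would not be reported anywhere. At the interim, the futility decision rests partly on an assessment of the secondary outcomes. There, one difference in incidence can appear as two supportive rows, once as the proportion and once as the duration.

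**Working it through.** **Inputs from the documents.** Tests are two-sided at 0.05 (SAP 4). SAP 10 gives about 240 evaluable subjects per arm. That figure reproduces: (2.2414 + 0.8416)² × (0.8×0.2 + 0.9×0.1) / 0.10² = 9.505 × 25 = 237.6, so 238, which the plan rounds to 240; then 240/0.9 = 267. It concerns the primary endpoint only. Neither document gives an incidence, mean, SD or power for the duration endpoints, so the rates below are assumptions. The nearest figures are background rates for COVID-19 in general in Protocol 2: 14% severe disease with hospitalisation and oxygen, 5% ICU. Asymptomatic outpatients may well be lower.

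**What the ANCOVA compares.** Let p be the proportion needing care and m the mean days among users. Mean days per subject is p × m.

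- Incidence 10% vs 5%, 7 days in both arms: 0.70 vs 0.35.
- Incidence 10% in both, 10 vs 5 days: 1.00 vs 0.50.
- Incidence 10% vs 5%, 7 vs 10 days: 0.70 vs 0.50.

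The first and third would favour treatment although no user has a shorter course.

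**What the Wilcoxon compares.** Let θ be the probability that a treated user's stay exceeds a placebo user's. Then P(treated > placebo) − P(treated < placebo) = (p₁ − p₀) + p₀p₁(2θ − 1). At 10% in both arms the duration term is at most 0.10 × 0.10 = 0.01 in size, whatever the durations. Halving incidence contributes 0.05 − 0.10 = −0.05. Incidence dominates.

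**Hodges-Lehmann.** This is the median of all between-arm differences. If 86% of each arm are zeros (the 14% background rate), 0.86² = 74% of the differences are exactly 0, so the estimate is 0 days.

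**Simulation.** 240 per arm; user durations gamma with mean 7 and SD 5, rounded up to whole days. A two-sample t test stands in for the ANCOVA without covariates.

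| Incidence (placebo vs active) | User mean days | Mean test | Wilcoxon |
|---|---|---|---|
| 1% vs 0.5% | 7 vs 7 | about 3% | about 7% |
| 2% vs 1% | 7 vs 7 | about 10% | about 14% |
| 5% vs 2.5% | 7 vs 7 | about 23% | about 29% |
| 10% vs 5% | 7 vs 7 | about 42% | about 56% |
| 10% vs 10% | 10 vs 5 | about 40% to 46% | about 5% |
| 10% vs 5% | 7 vs 10 | about 16% to 18% | about 51% to 55% |

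The ranges are the spread between separate runs. With equal arms all tests reject about 5%. In the 10% vs 5% row with equal durations, the incidence chi-square rejects about 55%, almost the same as the Wilcoxon.

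**Second set of assumptions.** 267 per arm; gamma with shape 2.5 and mean 8 days; placebo incidence 2% / 5% / 10% / 14%.

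- Incidence halved, durations equal: mean test 12 / 26 / 50 / 63%; Wilcoxon 14 / 32 / 60 / 77%; chi-square 14 / 33 / 60 / 77%.
- Duration halved, incidence equal: mean test 8 / 21 / 47 / 68%; Wilcoxon 5 / 6 / 6 / 7%; a Wilcoxon among users only 20 / 66 / 94 / 99%.
- Incidence halved, duration doubled (6 to 12 days): mean test 8 / 7 / 6 / 7%, because the effects cancel; Wilcoxon 15 / 30 / 56 / 70%.

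The Hodges-Lehmann estimate was 0 in every simulated trial checked.

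**The case against.** The plan has a good defence. Protocol 9.1 assigns all efficacy analyses to the mITT population, so keeping never-users follows the stated rule. The zero rule is open, and the SAP 6.2 headings are not themselves conditional. Users are selected after randomisation, so a users-only test would not be a randomised comparison. The Wilcoxon is only a sensitivity analysis. These endpoints are secondary and unadjusted (SAP 4.5), and the only interim formula is conditional power for the primary endpoint. All of this stands, and it is why the tests should stay.

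Two stronger readings are tempting. A reader might infer that the duration tests reject mainly because incidence differs. That fits the Wilcoxon but not the ANCOVA, which responds about equally to halving either component (26% vs 21% at 5% incidence, 63% vs 68% at 14%). A reader might also take the rejection rates with equal user durations as inflated type I error. The documents state no null hypothesis for these endpoints, and for mean days per subject the arms do differ in those scenarios, so the rejections are power.

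The defence does not remove the mismatch. Results are reported under the endpoint's name, that name is conditional on need, and no planned table shows duration among users.

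**Conclusion.** The point holds as a mismatch between endpoint and analysis. All four endpoints are named for users and analysed as days per mITT subject, with zeros and with days after death. A significant result is not evidence of a shorter course in those requiring care. The main ANCOVA mixes incidence and duration. The Wilcoxon is close to a second incidence test, and its accompanying estimate would be 0 days.

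The size depends on incidences that the documents do not give. With equal user durations, rejection runs from about 3% (mean test) and 7% (Wilcoxon) at 1% vs 0.5% to about 42% and 56% at 10% vs 5%. The direction of the finding rests on the algebra above, not on those rates. The simulations leave out covariates and the death rule. The primary analysis is untouched. This should be corrected, because it governs what may be concluded from four named endpoints and how they are read at the interim.

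**What to change.** Keep the zero-inclusive randomised comparison and the tests as they are. In SAP 2.2.2, 6.2 and 9, and in Protocol 4.1.2, 7.1.2 and 9.3 at the next amendment:

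1. Rename the endpoints *days on supplemental oxygen / in hospital / in ICU / on invasive ventilation through Day 29 per mITT subject (0 if none; days after death counted as specified in SAP 6.2)*.
2. Add one descriptive table per endpoint among users, by arm: n, median and range of observed days, deaths shown separately, no p-value.
3. State that a difference in days does not by itself show a shorter course in those requiring care.
4. State that at the interim these four rows are not independent of the corresponding proportions.

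The cost is wording and four small tables, with no new data. The sponsor gives up a claim of shorter duration among those requiring care.
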